Appendix 3.3. Study and Site Closure

Appendix 3.3.1. Discontinuation of Study Sites

Study site participation may be discontinued if Eli Lilly Japan, the investigator, or the ERB of the study site judges it necessary for medical, safety, regulatory, or other reasons consistent with applicable laws, regulations, and GCP.

Appendix 3.3.2. Discontinuation of the Study

The study will be discontinued if Eli Lilly Japan judges it necessary for medical, safety, regulatory, or other reasons consistent with applicable laws, regulations, and GCP.

Appendix 3.4. Publication Policy

The publication policy for Study I1F-JE-RHCV is described in the letters of agreement between the sponsor and the investigators and institutions.

Appendix 4. Hepatic Monitoring Tests for Treatment-Emergent Abnormality

Selected tests may be obtained in the event of a treatment-emergent hepatic abnormality and may be required in follow-up with patients in consultation with the Lilly, or its designee, clinical research physician.

Hepatic Monitoring Tests

Hepatic Hematology^a

Hemoglobin
 Hematocrit
 RBC
 WBC
 Neutrophils, segmented
 Lymphocytes
 Monocytes
 Eosinophils
 Basophils
 Platelets

Hepatic Chemistry^a

Total bilirubin
 Direct bilirubin
 Alkaline phosphatase
 ALT
 AST
 GGT
 CPK

Haptoglobin^a

Hepatic Coagulation^a

Prothrombin Time
 Prothrombin Time, INR

Hepatic Serologies^{a,b}

Hepatitis A antibody, total
 Hepatitis A antibody, IgM
 Hepatitis B surface antigen
 Hepatitis B surface antibody
 Hepatitis B Core antibody
 Hepatitis C antibody
 Hepatitis E antibody, IgG
 Hepatitis E antibody, IgM

Anti-nuclear antibody^a

Alkaline Phosphatase Isoenzymes^a

Anti-smooth muscle antibody (or anti-actin antibody)^a

Abbreviations: ALT = alanine aminotransferase; AST = aspartate aminotransferase; CPK = creatine phosphokinase; GGT = gamma-glutamyl transferase; Ig = immunoglobulin; INR = international normalized ratio; RBC = red blood cells; WBC = white blood cells.

^a Assayed by Lilly-designated or local laboratory.

^b Reflex/confirmation dependent on regulatory requirements and/or testing availability.

Appendix 5. Tests for Allergic Reactions and Hypersensitivity Events

Selected tests may be obtained in the event of anaphylaxis or generalized urticaria.

Hypersensitivity Tests^a

| | |
|--|---------------------------------------|
| Anti-LY2439821 antibodies (immunogenicity) | Tryptase |
| LY243821 serum concentration | N-methylhistamine |
| | Drug Specific IgE ^b |
| | Basophil Activation Test ^b |
| | Complements |
| | Cytokine Panel |

Abbreviations: IgE = Immunoglobulin E.

^a Assayed by Lilly-designated laboratory.

^b Basophil Activation test will be performed if a drug specific IgE assay is unavailable.

Appendix 6. List of Excluded Medications and Procedures

| Excluded Medications |
|---|
| IV antibiotics for an infection within 12 weeks prior to baseline |
| Systemic nonbiologic psoriasis therapy with the exception of: 
 • oral corticosteroids, if average daily doses are not greater than 10 mg/day of prednisone or its equivalent. • all topical treatment • methotrexate or oral retinoids administered before and during the study if doses are not greater than that of baseline. • cyclosporine and Apremilast if daily doses are not greater than that of baseline • Granulocyte-monocyte adsorption apheresis (GMA): use of GMA is allowed. |
| Concurrent use of any biologic agent |
| Previous treatment with ixekizumab |
| Live vaccination within 12 weeks prior to baseline (Week 0; Visit 2), or 
 • intend to have a live vaccination during the course of the study or within 12 months of completing treatment in this study, or • have participated in a vaccine clinical study within 12 weeks prior to baseline. |
| Vaccination with Bacillus Calmette-Guerin (BCG) within 12 months prior to baseline (Week 0; Visit 2), or 
 • intend to have this vaccination with BCG during the course of the study, or • within 12 months of completing treatment in this study. |
| Excluded Procedures |
| Have received phototherapy at the day of baseline (Week 0; Visit 2) and during the course of the study. |
| Have donated more than 400 ml of blood (for patients weighing ≥ 50 kg), or 
 • 200 ml of blood (for patients weighing < 50 kg), or • plasmapheresis/platelet apheresis within 30 days prior to study entry, or plan to donate blood during the study. |
| Excessive sun exposure or use of tanning booths for at least 4 weeks prior to baseline (Week 0; Visit 2) and during the study. |

Leo Document ID = e6d41fb9-3470-4c34-a272-74b8ebb854cf

Approver: PPD
Approval Date & Time: 01-Feb-2019 03:01:24 GMT
Signature meaning: Approved

Approver: PPD
Approval Date & Time: 01-Feb-2019 03:32:52 GMT
Signature meaning: Approved

Approver: PPD
Approval Date & Time: 01-Feb-2019 11:25:36 GMT
Signature meaning: Approved

### 3. Revision History

Statistical Analysis Plan (SAP) Version 1 was approved prior to first patient visit.

SAP Version 2 was approved prior to the final analysis. The overall changes incorporated in Version 2 are as follows:

- 1) Section of protocol deviation was updated to refer to the latest version of Trial Issue Management Plan (TIMP).
- 2) Race and race subcategory were added to the section of demographics and baseline characteristics.
- 3) Section of historical illnesses and preexisting conditions was added.
- 4) Summary of treatment compliance as continuous variable was added to the section of treatment compliance.
- 5) Wording was slightly updated to clarify the definition of primary analysis of the primary endpoint in the section of primary outcome and methodology.
- 6) Minor grammatical or formatting changes were made.

### 4. Study Objectives

Objectives	Endpoints

Primary
 
 
To assess the efficacy of ixekizumab Q2W beyond Week 12 in patients with generalized pustular psoriasis (GPP) and erythrodermic psoriasis (EP)
 
	
 
Number of patients who improved Global Improvement Score (GIS) at least 1 point from Week 12 through Week 20 and with <math>\leq 2</math> of GIS
 

Secondary
 
 
To assess the efficacy of ixekizumab Q2W beyond Week 12 in patients with GPP and EP
 
To assess the health outcomes of ixekizumab Q2W beyond Week 12 in patients with GPP and EP
 
To evaluate the potential development of anti-ixekizumab antibodies of ixekizumab Q2W beyond Week 12 in patients with GPP and EP
 
	
The following endpoints will be assessed at each scheduled visit after Week 12:
 
 
Number of patients with each GIS grade (1: Resolved, 2: Improved, 3: Unchanged, 4: Worsened)
 
Number of patients who achieved sPGA (0, 1) and sPGA (0)
 
Number of patients who achieved PASI 75, PASI 90, and PASI 100 from baseline
 
Change from baseline, and percent improvement from baseline in PASI
 
Change from baseline in PSSI in patients with scalp involvement at baseline, and percent of BSA involvement of Psoriasis
 
Change from baseline in DLQI total score and domains, and Itch NRS score
 
Number of patients who achieved DLQI (0, 1) and DLQI (0)
 
Number of patients who achieved Itch NRS <math>\geq 4</math> point reduction from baseline for patients who had baseline Itch NRS <math>\geq 4</math>
 
Number of patients who developed treatment-emergent anti-ixekizumab antibody (TE-ADA) and neutralizing anti-ixekizumab antibody (NAb)
 
 
GPP ONLY
 
 
Change from baseline on assessment of Generalized Pustular Psoriasis Severity Index at Week 12 and Week 20/ETV.
 

Note: Global improvement scores will be assessed in the four grades by comparing the psoriatic findings: (1) resolved, (2) improved, (3) unchanged, and (4) worsened. The global improvement score is assessed based on the comparison of the psoriatic findings, sPGA, PASI score, and other evaluations with those at the baseline. Abbreviations: BSA = body surface area; DLQI = Dermatology Life Quality Index; EP = erythrodermic psoriasis; GIS = Global Improvement Score; GPP = generalized pustular psoriasis; NAb = neutralizing anti-ixekizumab antibody; NRS = Numeric Rating Scale; PASI = Psoriasis Area and Severity Index; PASI 75 = at least a 75% improvement from baseline in PASI score; PASI 90 = at least a 90% improvement from baseline in PASI score ; PASI 100 = a 100% improvement from baseline in PASI score; PSSI = Psoriasis Scalp Severity Index; Q2W = every 2 weeks; sPGA = static Physician Global Assessment; TE-ADA = treatment-emergent anti-drug antibody.

## 5. Study Design

### 5.1. Summary of Study Design

Study I1F-JE-RHCV is a multicenter, open-label, post marketing clinical trial to evaluate the efficacy and safety of ixekizumab Q2W beyond Week 12 until Week 20 in patients with GPP and EP.

The study consists of 3 periods:

- **Period 1:** Screening Period (Visit 1) lasting from 7 to 30 days prior to Period 2 (baseline; Week 0; Visit 2)

Study investigator(s) will review patient history and screening test results to determine if the patient meets all inclusion and none of the exclusion criteria to qualify for participation in the study.

- **Period 2:** Induction Dosing Period from Week 0 (Visit 2) to Week 12 (Visit 6)

All eligible patients will be administered 160 mg ixekizumab as 2 SC injections at Week 0 (baseline; Visit 2) followed by 80 mg as 1 injection at Week 2, 4, 6, 8 and 10.

- **Period 3:** Maintenance Dosing Period from Week 12 to Week 20

Responders (GIS = 1 at Week 12) will complete the study.

Inadequate responders (GIS  $\geq 2$  at Week 12 and based on investigators' discretion) will continue to use ixekizumab 80 mg Q2W during Period 3. If patients show a therapeutic response (GIS = 1) with 80 mg Q2W after Week 12, the patient will complete the study. Patients who complete the study before Week 20 will have an early termination visit (ETV) instead of the original scheduled visit.

Figure RHCV.5.1 illustrates the study design.

[figure not shown]

Figure RHCV.5.1. Illustration of study design for Clinical Protocol I1F-JE-RHCV.

## 5.2. Determination of Sample Size

A total of 12 patients will be enrolled so that at least 5 patients with EP and 5 patients with GPP who are inadequate responders ( $\text{GIS} \geq 2$  at Week 12 and based on investigators' discretion) will continue to use ixekizumab beyond Week 12. Additional enrollment may occur and the sample size may be increased, if no GPP or EP patients enter into Period 3 (Maintenance Dosing Period) of the study.

The sample size is based on the following:

- In the I1F-JE-RHAT (RHAT) study, 5 GPP and 8 EP patients were enrolled. One GPP patient achieved  $\text{GIS} = 1$  (resolved) at Week 12 and the other 4 GPP patients achieved  $\text{GIS} = 2$  (improved). One EP patient achieved  $\text{GIS} = 1$  at Week 12 and 7 EP patients achieved  $\text{GIS} = 2$ . Although the sample size is very small, based on the result of RHAT study, it is assumed that approximately 5 patients at maximum may not achieve  $\text{GIS} = 1$  at Week 12 and may continue ixekizumab Q2W beyond Week 12 based on the investigators' discretion.
- The sample size is determined based on the feasibility in Japan. The prevalence rate of these patients is very low in Japan and it is also difficult to conduct a placebo-controlled study for these severe conditions (Umezawa et al. 2003, Rosenbach et al. 2010).

## 5.3. Method of Assignment to Treatment

Patients are assigned to treatment and will receive their assigned treatment as outlined in the protocol Section 7.1.

## 6. A Priori Statistical Methods

### 6.1. General Considerations

Statistical analysis of this study will be the responsibility of Eli Lilly Japan.

Efficacy, health outcomes and safety analyses for Period 2 will be conducted on the largest analysis set (Full Analysis Set [FAS]), defined as the set of patients with GPP and EP separately who receive at least 1 dose of study treatment in Period 2 (FAS Population). Efficacy, health outcomes and safety analyses for Combined Periods 2 and 3 will be conducted based on patients with GPP and EP separately who receive at least 1 dose of study treatment in Period 3 (Maintenance Dosing Period Population) although the protocol stated that these analyses will be conducted only for Period 3 on the Maintenance Dosing Period Population.

Baseline for efficacy, health outcomes, and safety analyses in Period 2 and Combined Periods 2 and 3 is defined as the last available value before the first dose in Period 2; in most cases, it will be the value recorded at Week 0 (Visit 2).

Change from baseline will be calculated as the value at the visit of interest minus the baseline value. If all baseline values are missing for a particular variable, then the change from baseline and the percent improvement from baseline will not be calculated.

In the analysis of adverse events for Period 2 and Combined Periods 2 and 3, all pre-existing conditions recorded at Visit 1 and any on-study adverse events recorded prior to the first dose in Period 2 will be used as baseline events.

As this is a single arm study with very small sample size, no statistical inference will be performed.

Continuous data will be summarized in terms of the mean, standard deviation (SD), minimum, maximum, median, and number of observations. The minimum and maximum will be reported to the same number of decimal places as the raw data recorded in the database. The mean and median will be reported to 1 more decimal place than the raw data recorded in the database. The SD will be reported to 2 more decimal places than the raw data recorded in the database. In general, the maximum number of decimal places reported shall be 4 for any summary statistics. Categorical data will be summarized as frequency counts.

The statistical analyses will be performed using SAS® Version 9.4 or higher.

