### **6.11.1. Primary Outcome and Methodology**

The primary analysis is to assess the efficacy of ixekizumab 80 mg Q2W beyond Week 12 in patients with GPP and EP separately, by presenting the number of patients who decreased their GIS by at least 1 point from Week 12 through Week 20 and with  $\leq 2$  of GIS at any visit of Week 14 (Visit 7), Week 16 (Visit 8), Week 18 (Visit 9), Week 20 (Visit 10), or ETV. (Analysis population: Maintenance Dosing Period Population).

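### The primary result is planned as a bare count in about five patients per disease, possibly fewer, with no interval to show how imprecise it is

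*SAP*

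**What the plan says.** SAP 6.11.1 gives the primary analysis for each disease on its own: "by presenting the number of patients who decreased their GIS by at least 1 point from Week 12 through Week 20". A patient must also reach a GIS of 2 or lower at any visit from Week 14 to Week 20 or at the early termination visit. The denominator is named: "Analysis population: Maintenance Dosing Period Population", that is, patients with at least one dose in Period 3.

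SAP 6.1 fixes the form of the result: "Categorical data will be summarized as frequency counts". It gives two reasons for going no further: "As this is a single arm study with very small sample size, no statistical inference will be performed". Protocol 10.3.1 and the Protocol Synopsis carry the same statement, and SAP 6.2 repeats it as the reason for not adjusting for covariates. No confidence or credible interval is planned anywhere in either document.

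On size, SAP 5.2 says: "A total of 12 patients will be enrolled so that at least 5 patients with EP and 5 patients with GPP". The five in each disease are to be inadequate responders at Week 12 who go on into Period 3. SAP 6.11 also plans by-patient listings of each efficacy measure.

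**The concern.** The two reasons given bear on hypothesis testing: there is no comparator, and with so few patients a test would have little power. Neither bears on whether the observed proportion should be shown with its precision. An exact binomial interval needs no control arm, no large-sample approximation, no success threshold and no multiplicity rule, so it fits a descriptive aim. It is also most informative where the count is small.

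The trial fulfils a commitment to the Japanese regulator, and Protocol 3.2 says that it should support consistent dosing guidance in two indications that had no data on two-weekly dosing beyond Week 12. A reader of the report will want to know which response rates the counts are compatible with. A bare 5/5 or 3/5 does not say, and may be taken as firmer evidence than it is.

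**Working it through.** **Inputs from the documents (SAP 5.2).** In the prior study, "5 GPP and 8 EP patients were enrolled". At Week 12, 4 of the 5 GPP patients (80%) and 7 of the 8 EP patients (87.5%) had not reached GIS = 1. Pooled, that is 11/13 = 84.6%. The target is 5 per disease, 10 in all. The SAP states no confidence level, power or precision target; it bases the number on feasibility.

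**Step 1: the plan's own figure of 12.** The SAP gives no formula. Dividing the target by the prior-study rates gives:
- pooled: 10 / (11/13) = 11.8, rounded up to 12;
- by disease: 5/0.80 = 6.25, so 7, plus 5/0.875 = 5.7, so 6; total 13.

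So 12 is consistent with the prior study, and 12 × 11/13 = 10.2 patients would be expected in Period 3.

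**Step 2: the likely denominators.** Assume a 6:6 split, the prior-study rates as true, no dropout before Week 12, and entry into Period 3 by every patient with GIS of 2 or more.
- Expected: 6 × 0.80 = 4.8 GPP and 6 × 0.875 = 5.25 EP.
- P(at least 5 GPP) = 6 × 0.80⁵ × 0.20 + 0.80⁶ = 65.5%.
- P(at least 5 EP) = 6 × 0.875⁵ × 0.125 + 0.875⁶ = 83.3%.
- P(at least 5 in both) = 0.655 × 0.833 = 55%. It is 44% with 7 GPP and 5 EP, and 31% with 5 GPP and 7 EP.

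About five per disease is therefore right as an expectation, but fewer than five in at least one disease is quite possible. Dropout or investigator discretion over entry would lower the numbers further. SAP 5.2 allows extra enrolment only when no patient with a disease enters Period 3, so one to four would not trigger it.

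**Step 3: exact intervals.** The level (two-sided 95%) and the method are assumptions of this check. The Clopper-Pearson limits for x of n are the 2.5% quantile of Beta(x, n − x + 1) and the 97.5% quantile of Beta(x + 1, n − x). For x = n the lower limit is 0.025^(1/n); for x = 0 the upper limit is 1 − 0.025^(1/n).

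| Count | Observed | Exact 95% interval |
|---|---|---|
| 0/5 | 0% | 0% to 52.2% |
| 3/5 | 60% | 14.7% to 94.7% |
| 4/5 | 80% | 28.4% to 99.5% |
| 5/5 | 100% | 47.8% to 100% |
| 4/4 | 100% | 39.8% to 100% |
| 6/6 | 100% | 54.1% to 100% |

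The interval spans 52 points for 5/5 and 80 points for 3/5.

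**Step 4: sensitivity of the 5/5 lower limit.** A one-sided exact 95% bound is 0.05^(1/5) = 54.9%. The Wilson two-sided lower limit is 56.6%. The limit moves across 50% with the method, but the interval is wide in every case. As a check that needs no interval method, a true rate of 50% gives 5/5 with probability 0.5⁵ = 3%, 60% gives 0.6⁵ = 8%, and 70% gives 0.7⁵ = 17%.

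**The case against.** **The choice is open and consistent.** Both documents declare descriptive-only reporting and give the reasons. The SAP mentions the very small sample repeatedly, names the denominator, tabulates GIS grades by visit (6.11.2) and lists every patient. Anyone with the count and N can compute the interval. All of this stands. It makes the point a reporting weakness, not an error or a contradiction, and how readers will take a bare count cannot be shown from the documents.

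**An interval could lend false rigour.** Patients enter Period 3 on their Week 12 GIS and the investigator's discretion, the rating is open-label and made against baseline, response counts at any later visit, and there is no control. A binomial interval covers sampling error only. This also stands, and is why the interval needs a label and a statement of its limits. A bare count has the same defects and leaves out the sampling error as well.

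**The stakes are limited.** Protocol 3.2 says that continued two-weekly dosing after an inadequate response was already approved in August 2018, and no decision is tied to a response-rate threshold. That is fair and keeps the severity low.

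**Stronger readings that the documents do not support.**
- A reader might infer that even complete success cannot rule out a true rate below one half. That holds only for n = 5 or fewer with a two-sided 95% Clopper-Pearson interval; Step 4 and the 6/6 row show it failing under other reasonable choices.
- A reader might infer that intervals are needed to guard a comparison of GPP with EP. No such comparison is planned, and two separate intervals would not test one.
- A reader might want intervals for the binary secondary endpoints too. That would need decisions on the population at Week 12 and on how patients who complete early with GIS = 1 are handled at later visits, and it would add many intervals that say little.

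**Conclusion.** The point holds as a minor one. The primary result is a count in about five patients per disease, possibly fewer, with no measure of precision. The stated reasons justify leaving out hypothesis tests but not a descriptive interval. At five patients, the exact 95% interval runs from 14.7% to 94.7% for 3/5 and from 47.8% to 100% for 5/5. These figures rest on an assumed n of 5, a two-sided 95% level and the Clopper-Pearson method. The conclusion that the uncertainty is wide does not depend on those choices; the exact limits do.

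SAP 5.2 also sets a target of at least five per disease beside a rationale in which "it is assumed that approximately 5 patients at maximum may not achieve" GIS = 1. The two statements should be reconciled, because they describe the denominator of the primary result.

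**What to change.** - **SAP 6.1, with matching wording in 6.2:** replace the exclusion of statistical inference with an exclusion of hypothesis testing.
- **SAP 6.11.1:** report n/N with a two-sided exact (Clopper-Pearson) 95% interval for the primary endpoint, for GPP and EP separately, in the Maintenance Dosing Period Population.
- **Label:** call the interval descriptive, and state that it does not account for selection into Period 3, the any-visit response definition, open-label rating or the lack of a control.
- **Protocol:** record the difference from the wording in Protocol 10.3.1 and the Synopsis in the SAP or the clinical study report. Protocol 10.3.1 requires an amendment only for a change to a principal feature; the endpoint, population and counts stay the same here. SAP 6.1 already records another departure from the protocol in this way.

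The cost is a few sentences and standard software output. The downside is that the intervals will be wide and will make the result look less favourable than a bare count.

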### 6.2. Adjustments for Covariates

No statistical adjustments for covariates will be made as statistical inference will not be performed in this single arm study with very small sample size.

### 6.3. Handling of Dropouts or Missing Data

The methods for imputation of missing data to be used in this study are in accordance with the precedent set in other Phase 3 psoriasis trials (Leonardi et al. 2008; Papp et al. 2008) and ixekizumab Phase 3 studies.

### **6.3.1. Nonresponder Imputation (NRI)**

Categorical binary efficacy and health outcomes variables will be summarized using a nonresponder imputation (NRI) method. Patients will be considered a nonresponder if they do not meet the clinical response criteria or have missing clinical response data at the scheduled time point. All patients who discontinue study treatment at any time prior to the scheduled visit for any reason will be defined as nonresponders regardless of study continuation without study treatment at the visit. Enrolled patients without at least 1 post-baseline observation will also be defined as nonresponders.

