5.1. Overall Design

Study I1F-JE-RHCV is a multicenter, open-label, post marketing clinical trial to evaluate the efficacy and safety of ixekizumab Q2W beyond Week 12 until Week 20 in patients with GPP and EP.

The study consists of 3 periods:

- **Period 1:** Screening Period (Visit 1) lasting from 7 to 30 days prior to Period 2 (baseline; Week 0; Visit 2)

Study investigator(s) will review patient history and screening test results to determine if the patient meets all inclusion and none of the exclusion criteria to qualify for participation in the study.

- **Period 2:** Induction Dosing Period from Week 0 (Visit 2) to Week 12 (Visit 6)

All eligible patients will be administered 160 mg ixekizumab as 2 SC injections at Week 0 (baseline; Visit 2) followed by 80 mg as 1 injection at Week 2, 4, 6, 8 and 10.

- **Period 3:** Maintenance Dosing Period from Week 12 to Week 20

Responders (GIS = 1 at Week 12) will complete the study.

Inadequate responders (GIS ≥ 2 at Week 12 and based on investigators' discretion) will continue to use ixekizumab 80 mg Q2W during Period 3. If patients show a therapeutic response (GIS = 1) with 80 mg Q2W after Week 12, the patient will complete the study. Patients who complete the study before Week 20 will have an early termination visit (ETV) instead of the original scheduled visit.

Patients discontinuing from the study treatment who have received at least 1 dose of investigational product will continue to the ETV.

Ixekizumab will not be made available after conclusion of the study to patients.

Study governance considerations are described in detail in [Appendix 3](#).

[Figure RHC.V.1](#) illustrates the study design.

[figure not shown]

Figure RHCV.1. Illustration of study design for Clinical Protocol I1F-JE-RHCV.

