### **6.3.2. Last Observation Carried Forward (LOCF)**

Continuous efficacy and health outcomes variables will be summarized using a last observation carried forward (LOCF) method. For patients discontinuing study treatment for any reason, the last non-missing post-baseline observation before the missing data will be carried forward to the corresponding time point for evaluation. Enrolled patients without at least 1 post-baseline observation will not be included for evaluation.

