### **6.11.3. Other Secondary Efficacy Analyses**

For other efficacy measures, the following endpoints will be summarized descriptively at each scheduled visit for Period 2 and for Combined Periods 2 and 3, respectively (Analysis population: FAS Population for Period 2, Maintenance Dosing Period Population for Combined Periods 2 and 3):

- Number of patients who achieve sPGA (0, 1) and sPGA (0)
- Number of patients who achieve PASI 75, PASI 90, and PASI 100 from baseline
- Change from baseline, and percent improvement from baseline in PASI
- Change from baseline in PSSI in patients with scalp involvement at baseline
- Change from baseline in percent of BSA involvement of psoriasis.

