		DLQI work and school domain	Sum of responses of questions question #7A and #7B: #7A. Has your skin prevented you from working or studying? #7B. If No: how much has your skin been a problem at work or studying?	If the answer to question #7A is missing, this domain is missing. If #7A is No, and #7B is missing, this domain is missing.

Measure	Description	Variable	Derivation / Comment	Imputation Approach if with Missing Components
		DLQI personal relationships domain	Sum of responses of questions #8 and #9: #8. How much has your skin created problems with your partner or any of your close friends or relatives? #9. How much has your skin caused any sexual difficulties?	If one question in a domain is missing, that domain is missing.
		DLQI treatment	Response of question #10: #10. How much of a problem has the treatment for your skin been, for example by making your home messy, or by taking up time?	If one question in a domain is missing, that domain is missing.
		DLQI total score	A DLQI total score is calculated by summing all 10 question responses, and has a range of 0 to 30 (less to more impairment) (Finlay and Khan 1994; Basra et al. 2008).	If two or more questions are missing, the total score is missing. Note: #7B could be a valid missing while #7A is not “No.” That is, #7 should be considered as one question.
		DLQI (0,1)	A DLQI (0,1) response is defined as a post-baseline DLQI total score of 0 or 1. A DLQI total score of 0 to 1 is considered as having no effect on a patient’s HRQoL (Khilji et al. 2002; Hongbo et al. 2005).	Missing if DLQI total score is missing
		DLQI (0)	A DLQI (0) response is defined as a post-baseline DLQI total score of 0.	Missing if DLQI total score is missing
		DLQI total score and domain scores change from baseline	Calculated as: observed DLQI (total score or domain scores) – baseline DLQI (total score or domain scores)	Missing if baseline or observed value is missing

For health outcomes measures, the following endpoints will be summarized descriptively at each scheduled visit for Period 2 and for Combined Periods 2 and 3, respectively (Analysis population: FAS Population for Period 2, Maintenance Dosing Period Population for Combined Periods 2 and 3):

- Change from baseline in Itch NRS score
- Number of patients who achieve Itch NRS  $\geq 4$  point reduction from baseline for patients who had baseline Itch NRS  $\geq 4$

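### The nonresponder rule has no exception for patients who must leave on response (GIS = 1), so later by-visit binary tables score them as failures

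*SAP*

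**What the plan says.** SAP 6.3.1 governs all binary efficacy and health outcomes variables. A patient is "considered a nonresponder if they do not meet the clinical response criteria or have missing clinical response data at the scheduled time point". It then adds: "All patients who discontinue study treatment at any time prior to the scheduled visit for any reason will be defined as nonresponders". No exception is listed.

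The design itself creates empty visits. Protocol 5.1 says: "If patients show a therapeutic response (GIS = 1) with 80 mg Q2W after Week 12, the patient will complete the study". SAP 5.1 repeats this and states: "Patients who complete the study before Week 20 will have an early termination visit (ETV) instead of the original scheduled visit". Neither document schedules any later visit for such a patient.

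The binary endpoints are tabulated by visit. In SAP 6.11.3 the "following endpoints will be summarized descriptively at each scheduled visit for Period 2 and for Combined Periods 2 and 3", and SAP 6.12 has the same layout: "For health outcomes measures, the following endpoints will be summarized descriptively at each scheduled visit". The combined-period tables use the Maintenance Dosing Period Population, which is everyone dosed at least once in Period 3 (SAP 6.1). Early completers therefore stay in it.

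For continuous variables, SAP 6.3.2 provides that, for patients who stop study treatment, "the last non-missing post-baseline observation before the missing data will be carried forward to the corresponding time point for evaluation".

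**The concern.** The missing value here is a direct result of response. A patient leaves because GIS reached 1, has no data at the next scheduled visits, and is then counted as not responding at each of them. A reader of the Week 20 rows cannot separate a patient who was required to stop on response from one who failed.

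The SAP handles the same patient differently elsewhere. Section 6.7 counts the patient as completing Period 3. Section 6.9 calls the patient a responder. Section 6.11.1 accepts success at the ETV. The imputation sections do not mention the group.

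Two related rules are also unclear. Section 6.3.2 does not say whether carry-forward covers patients who complete on GIS = 1 or only those who discontinue. No explicit rule assigns ETV data to the visit it replaces, although the wording of SAP 5.1 points that way.

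The study is descriptive, without inference, so these counts are themselves the secondary results.

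**Working it through.** The plan gives no figure for this point, so there is nothing to reproduce. The check has five steps.

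**1. Does the rule catch the patient?** Exit at Week 14, 16 or 18 leaves every later scheduled visit without data. The missing-data clause of 6.3.1 alone then gives nonresponse. The treatment-discontinuation sentence can catch the same patient, but is not needed.

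**2. How does the primary analysis score the patient?** Entry to Period 3 requires GIS of 2, 3 or 4, and exit is at GIS = 1. The decrease is 1, 2 or 3 points with final GIS ≤ 2, so every such patient is a primary success by construction.

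**3. How many table entries are affected?** There are 8 binary endpoints: sPGA (0,1), sPGA (0), PASI 75, PASI 90, PASI 100, Itch NRS reduction ≥ 4, DLQI (0,1) and DLQI (0). Six are scheduled at Weeks 14, 16, 18 and 20. The two DLQI endpoints are not scheduled at Week 16 (Protocol Table RHCV.1). The maximum entries per patient are:

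| | Exit Week 14 | Exit Week 16 | Exit Week 18 |
|---|---|---|---|
| Later entries | 6×3 + 2×2 = 22 | 8×2 = 16 | 8×1 = 8 |
| Baseline Itch NRS below 4 | 5×3 + 2×2 = 19 | 7×2 = 14 | 7×1 = 7 |
| Distinct measures (sPGA, PASI, Itch NRS, DLQI) | 3×3 + 1×2 = 11 | 4×2 = 8 | 4×1 = 4 |
| All 8 endpoints, ETV not assigned to replaced visit | 22 + 8 = 30 | 16 + 6 = 22 | 8 + 8 = 16 |

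These are maxima. Several endpoints are nested, and an entry that was already a failure at exit is not changed.

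**4. What does it do to a count?** The plan aims for at least 5 patients per disease type in Period 3 (SAP 5.2). One patient is 1/5 = 20 percentage points. As an assumed example, take 5 patients and an endpoint scheduled at all four visits. One patient exits at each of Weeks 14, 16 and 18, each first meeting the criterion at exit, and the other two never respond.

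| | Week 14 | Week 16 | Week 18 | Week 20 |
|---|---|---|---|---|
| As written, ETV assigned to replaced visit | 1/5 | 1/5 | 1/5 | 0/5 |
| As written, ETV not assigned | 0/5 | 0/5 | 0/5 | 0/5 |
| Response at exit retained | 1/5 | 2/5 | 3/5 | 3/5 |

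The last row assumes that response persists after exit, which nobody observes. It shows the size of the gap, not the true Week 20 status.

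**5. Do the binary and continuous tables agree?** Assume 5 patients: one exits at Week 14 with 100% PASI improvement and four have 80% at Week 20. The nonresponder rule gives PASI 75 = 4/5. If carry-forward covers the early completer, the Week 20 mean is (100 + 4×80)/5 = 84.0% with n = 5, and all five values are at least 75%. If it does not, the mean is (4×80)/4 = 80.0% with n = 4, beside a count out of 5.

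**The case against.** The strongest reply is that the rule does not lower the number of responders actually observed at Week 20. In step 5 that number is 4 under the rule and 4 as observed. It becomes 5 only if response is carried past exit, where nothing is measured. Protocol 3.1 describes frequent relapse in these diseases, and Protocol 5.1 adds: "Ixekizumab will not be made available after conclusion of the study to patients". The SAP also plans frequency counts, so the percentage is a translation. This stands: the 20 points measure the gap to a last-on-study count, not to known Week 20 status. It does not answer the complaint that completion on response and failure fall into one unlabelled class.

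Second, the SAP generally separates completing from discontinuing, so the discontinuation sentence need not apply. That is fair, but the missing-data clause suffices.

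Third, the carry-forward and ETV points are ambiguities rather than errors. Section 6.3.2 opens with a general statement that continuous variables use carry-forward, and the number of observations is reported. This also stands, and the 30, 22 and 16 apply only if the likely ETV intent is not followed.

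Fourth, the by-patient listings and the disposition listing let a careful reader identify early completers. They do, but they leave the tabulated counts unflagged.

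Finally, the tables are secondary and the effect depends on early exits occurring. Both are true and limit the weight of the point.

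**Conclusion.** The concern holds and should be fixed. As written, SAP 6.3.1 scores an exit that the protocol requires on response in the same way as a treatment failure, and this conflicts with the patient's status in SAP 6.7, 6.9 and 6.11.1. The error lies in the scoring rule; it is not a known loss of a Week 20 responder.

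The 1-in-5 size rests on two assumptions: 5 patients in the disease group, and an early completer who met the binary criterion at exit. GIS = 1 does not by definition guarantee sPGA, PASI, Itch NRS or DLQI response. The documents give no rate of early exit, since the earlier RHAT study is reported at Week 12 only, so no expected frequency is derived. The four-grade GIS table is not binary and so falls outside the rule, but early completers simply disappear from its later rows.

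**What to change.** The exit rule itself stays as it is. The changes are to the SAP:

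- **6.3.1:** add *Patients who complete the study because GIS = 1 are not treated as missing or discontinued under NRI. ETV data are assigned to the scheduled visit that the ETV replaces.*
- **By-visit binary tables:** show *completed early, GIS = 1* as a separate category with its count.
- **Supplementary Week 20/ETV summary of each binary endpoint:** use the last on-study assessment for GIS = 1 completers, and NRI for all other missing data or discontinuations. The plan already uses this time point for the GPP Severity Index. A DLQI taken at an ETV that replaces Week 16 has no scheduled slot and appears only here.
- **GIS grade:** show the observed grade at Week 20/ETV with a row for missing or discontinued patients, without NRI.
- **6.3.2:** state whether GIS = 1 completers are carried forward, and print the number carried forward beside each mean. Any carry-forward of response beyond exit is supportive only.

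The cost is SAP wording, one visit-mapping rule, one extra row per by-visit table and one supplementary summary. No new data are needed, because the ETV already collects every measure. The drawback is that Week 20/ETV pools assessments from Week 14 to Week 20 and takes the exit value from patients selected for having responded, so it leans upward. It should therefore supplement the by-visit tables and always show the number of early completers.
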